5.4.3. After insertion of the pessary or beginning of the administration with vaginal progesterone capsules and until 28 weeks of gestation, participants in the 3 treatment groups will be monitored every 4 weeks at the most or more often, if the site has established so as a control standard. After 28 weeks, patients should be monitored every 2 weeks. At every control visit, procedures applicable to their prenatal control and a transvaginal ultrasound by standard technique will be performed (patients receiving vaginal capsules), if considered necessary by the physician, or transvaginal using the technique recently described (25) (in patients with medicated pessary) to measure and record cervical length. The occurrence of possible side effects, adherence to treatment, and visits or hospitalizations due to threat or preterm labor will also be recorded, as well as the existence of potential causes for *ex-post* exclusion from the study. In addition, concomitant medication will be recorded at each visit.

5.4.4 Management of participants consulting due to a threat or premature labor will be conducted according to the diagnostic and therapeutic guidelines of the Ministry of Health (MINSAL) (Clinical Guide for Preventing Preterm Birth - MINSAL 2010) and the respective hospital's Obstetrics and Gynecology Service. In these cases, the treating physician will be provided with information about the progesterone treatment the patient is receiving in the study, and the decision for her continuation in the clinical study will be made jointly as far as possible, since the opinion of the treating physician shall predominate.

5.4.5 Every case will be closed at 36 6/7 weeks of gestation, or at the time of preterm birth. Data on the birth, condition at birth, and evolution of infants born preterm will be analyzed, recording morbidity and mortality through the time of discharge from the hospital.

The participant's attending health team (physicians and midwives) will be informed in writing about the participation of these women in the study by means of an identification

card that will be given to every woman participating in the study. In the pregnancy card, participation of these subjects in the study will be emphasized by means of a self-adhesive sticker detailing their participation in one of the treatment groups (pessary or capsule) and recorded in the medical history.

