## **9 STATISTICS**

This project aims to conduct a randomized, open-label, controlled, clinical-exploratory phase II study evaluating the efficacy of a cerclage pessary containing one of 2 doses of sustained-release micronized progesterone for prevention of preterm birth, compared to the treatment method currently used by obstetrics-gynecology specialists, which comprises the administration of one daily capsule by vaginal route of 200 mg of progesterone. A total of

270 pregnant participants at risk of preterm birth will be enrolled, screened, and randomized to the 3 groups of treatment previously described. The number of patients listed ( $n = 270$ ) refers to the number of patients who effectively are enrolled and successfully complete the study. Therefore, an enrollment of at least 10% over that number (27 patients or more) should be considered due to the eventual withdrawal or early loss to follow-up of patients initially recruited.

As primary results, the proportions of spontaneous preterm delivery before gestation weeks 32 and 34 will be compared between the control group and the 2 groups with the pessaries containing different doses of progesterone. The risk of spontaneous preterm birth from the time of inclusion in the study through the gestation weeks 32 and 34 will be determined by a Kaplan-Meier analysis, where gestational age will be the time scale and spontaneous delivery will be the event; elective parturitions will be censored. For the purpose of this analysis, pregnancies will no longer be considered as high risk for the event if delivery occurs at the week of gestation 34 (34 0/7) or beyond.

As secondary outcomes, those qualitative variables in pregnant participants at risk of preterm birth will be evaluated, and the percentage distribution of acceptability responses or side effects recorded will be determined. For the quantitative variables (measurements of length and cervical angulation), the averages and standard deviations of the values found will be compared. Accordingly, each participant will work as her own control.

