this is in terms of decrease of the proportion of pregnancies with premature risk. In this way it will be determined the effective response to progesterone in the cerclage pessary through the occurrence of spontaneous delivery after 32 weeks but before 34 weeks of gestation. The evaluation of the error type 1 will be with a value of 0.05 for the type of variable being used.

As part of the exploratory analysis for the efficacy of treatments, the risk of spontaneous premature birth from the moment of inclusion in the study until the weeks 32 and 34 of gestation, will be determined with the Kaplan-Meier analysis, where the gestational age is the timeline, spontaneous delivery will be the event and elective deliveries will be censored. A singleton pregnant subject between 16 and 24 weeks of gestation will be eligible to participate in the study when she meets one of the following two conditions:

- Cervical length between 10 to 25 mm and without risk factors
- Cervical length greater or equal to 10 mm and with pre-existing risk factors in the immediate preceding pregnancy characterized by:
 - premature delivery before the week 35 (with a viable fetus)
 - premature rupture of membrane prior to week 35 (with a viable fetus)

There are two ways to measure the gestational age which are the following:

- Gestational Age according to DLNM (weeks)
- Gestational Age according to Transvaginal Ultrasound (weeks)

The time of gestational age will be evaluated through log-rank tests among treatments. The null hypothesis is stated as the no treatment differences in the gestational ages.

Kaplan-Meier (product limit) estimates of the gestational age distribution will be calculated and their corresponding 95% confidence interval (CI) will be presented: 25th percentile, mean, median, and 75th percentile.

The analysis will be performed for the two measurements of gestational time, considering the Transvaginal ultrasound the one most accurate.

For the purposes of this analysis, pregnancies will no longer be considered of high risk in the event birth takes place in week 34 (34 0/7) of gestation or more.

SECONDARY ANALYSIS

For some of the secondary variables, subjects will be their own controls in the following variables to evaluate and the following analysis are proposed:

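### The SAP plans a Kaplan-Meier mean gestational age without a cut-off; if follow-up stops at 34 0/7 weeks the mean is not identified, and cutting each curve at its own last event could rank the better arm lower

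*SAP*

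**What the plan says.** SAP section 10 (Primary Analysis) introduces the Kaplan-Meier work with "As part of the exploratory analysis for the efficacy of treatments". The risk of spontaneous premature birth, counted from inclusion "until the weeks 32 and 34 of gestation, will be determined with the Kaplan-Meier analysis". The time scale, the event and the censoring rule are then set out: "where the gestational age is the timeline, spontaneous delivery will be the event and elective deliveries will be censored". Arms are compared by log-rank: "The time of gestational age will be evaluated through log-rank tests among treatments". The estimates of the gestational-age distribution, with 95% confidence intervals, "will be presented: 25th percentile, mean, median, and 75th percentile".

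The section closes its account of this analysis by saying that "pregnancies will no longer be considered of high risk in the event birth takes place in week 34 (34 0/7) of gestation or more". Protocol section 9 has the same rule: "pregnancies will no longer be considered as high risk for the event if delivery occurs at the week of gestation 34 (34 0/7) or beyond".

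Neither document gives a restriction time for the mean, or says how to calculate it when a curve ends above zero. SAP section 5 names SAS 9.2 or later and no option. Protocol section 9.2 names other packages.

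**The concern.** A product-limit mean is the area under the survival curve. If the curve never reaches zero, the area must be stopped somewhere, and the answer depends on where. On a 34-week horizon every woman still pregnant at 34 0/7 is a non-event, so each arm's curve ends on a plateau.

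The percentiles fail visibly in that setting. The 25th percentile needs a quarter of women to have delivered before 34 weeks, the median half and the 75th percentile three quarters; otherwise the cell is not estimable. The mean does not fail visibly, because it prints a number whatever the event rate. If that number is the area up to the arm's own last event, it cannot exceed that event time. An arm with few events tends to have an earlier last event, so doing well can pull its mean down.

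At stake is how one summary reads. The stated null is no difference in gestational ages, so a reader may look to the mean gestational age first. It would appear for three arms, two ways of dating the pregnancy, and the PP and ITT sets: up to 3 × 2 × 2 = 12 cells.

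**Working it through.** **Inputs from the documents.** 90 women per arm (Protocol 9.1, SAP section 3); end of the risk period at 34 0/7 (SAP section 10, Protocol section 9); case closure at 36 6/7 (Protocol 5.4.5). The documents give no figure for the mean, so there is none to reproduce.

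**Assumptions.** No control rate is given, so I took 8% to 50%. The upper end is included because a 40% relative reduction gives 90 per arm at 80% power only with a control rate of about 51% (51% v 30.6%). Event times lie between 24 and 34 weeks, either uniform or with linearly rising density. Nobody is censored before 34.0.

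**Formula.** Without earlier censoring, for *d* events among *n* women and a cut-off *c* no earlier than the last event, the area is (sum of event times + (*n* − *d*) × *c*) / *n*.

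**Worked example, *n* = 90.** Capsules: 18 events evenly spaced from 26 to 33.8 weeks, sum 18 × 29.9 = 538.2. Pessary: 6 events evenly spaced from 26 to 32 weeks, sum 6 × 29 = 174.

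- Cut at the last event, capsules: (538.2 + 72 × 33.8) / 90 = 33.02 weeks.
- Cut at the last event, pessary: (174 + 84 × 32) / 90 = 31.80 weeks.
- Cut at 34.0, capsules: (538.2 + 72 × 34) / 90 = 33.18 weeks.
- Cut at 34.0, pessary: (174 + 84 × 34) / 90 = 33.67 weeks.

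The arm with a third of the events looks 1.2 weeks worse under the first rule and 0.5 weeks better under the second.

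**Simulation.** 20,000 trials per scenario. The table shows the share of trials in which the truly better arm has the lower mean; ranges are over the two timing shapes. Trials with an eventless arm are left out of the last-event column.

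| Control v pessary | Cut at own last event | Common cut at 34.0 |
|---|---|---|
| 8% v 4.8% | 58% | 22-24% |
| 10% v 5% | 59-60% | 14-15% |
| 20% v 12% | 39-43% | 11-13% |
| 30% v 18% | 22-25% | 5-7% |
| 40% v 24% | 11-14% | 3-4% |
| 50% v 30% | 5-6% | 1-2% |

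The right-hand column is not zero because the better arm can, by chance, have more events or earlier ones. The excess on the left is the truncation artefact.

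**Sensitivity to the horizon.** I kept the last-event cut-off but let the curves run on, assuming later births around 39 weeks (SD 1.6), 20% of them elective and censored; 4,000 trials per scenario, standard error about half a percentage point. At 10% v 5% the better arm ranks lower in 17-18% of trials with follow-up to 36 6/7 and 14-16% with all births, against 13-14% for the common 34-week cut in the same runs. At 20% v 12% the figures are 11-12%, about 10% and 10-11%. On these horizons the artefact has largely gone.

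**The case against.** The strongest reply is that the 34-week stop is only one reading. In SAP section 10 the event is spontaneous delivery without a gestational limit, and only elective deliveries are named as censored. The 34 0/7 sentence can be taken as a risk classification. A gestational-age distribution with quartiles suits a curve over all births better. Later data will exist: "Every case will be closed at 36 6/7 weeks of gestation, or at the time of preterm birth", and SAP Table 1 records gestational age with the birth data. This stands in part. The stated horizon of weeks 32 and 34 and the 34 0/7 rule favour the 34-week reading but do not exclude the other, and on the other the ranking problem is negligible.

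Second, cutting at the last event is in neither document. That stands in full. A reader might infer that the SAP, as planned, will show an effective pessary with a lower mean. The text does not support this: it fixes no cut-off. The established defect is that silence.

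Third, the size depends on the event rate. That stands too. The Rationale (Protocol section 2, on preventing preterm birth) says that 55-60% of women with a shortened cervix still delivered by week 34 despite progesterone; near such rates the reversal is rare. Lower rates remain plausible, since Protocol 4.1.1 also admits women with a previous event and any cervix of at least 10 mm.

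Fourth, nothing formal uses the mean. The arms are compared by CMH tests, odds ratios and the log-rank test, and no difference in means is planned. This stands, and it sets the severity.

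**Conclusion.** The concern holds in a narrow, conditional form and is minor. If follow-up ends at 34 0/7, the plan lists a statistic that its own horizon cannot identify, and the value reported would depend on an unstated choice. If that choice were each arm's last event, the ranking could reverse: often at low event rates, seldom at rates near 50%.

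The size rests on four assumptions: the 34-week horizon, the last-event cut-off, the event rates and the event timing. A stronger inference, that the trial's efficacy conclusion is at risk, is not supported. The CMH and log-rank tests do not use the mean, and a misleading mean would stand beside proportions and odds ratios that show the true direction.

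**What to change.** In SAP section 10:

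- State that follow-up for the Kaplan-Meier analysis is censored at 34 0/7 weeks. If a longer horizon is intended, say so and name it.
- Replace the mean with the restricted mean gestational age to 34 0/7, with the same cut-off in all three arms, or drop the mean.
- Add the Kaplan-Meier risk of spontaneous delivery at 32 and at 34 weeks with 95% confidence intervals. This is what the analysis is said to determine, yet it is missing from the listed summaries.

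Differences in restricted mean between each pessary arm and the capsules are optional. The cost is a sentence or two in the SAP and a few lines of code, with no new data and no change to the primary test.

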## 5.8. Recording, quality control, and data management

Information about the characteristics of the participants, including demographics (race, age, parity, measures for calculation of body mass index [BMI]), and the medical and obstetrical records will be obtained directly from the participants and recorded in the study file. Information about the outcome of the pregnancy will be obtained from the hospital's medical records file or treating physician. Medical records of participants experiencing preterm birth labor before weeks 32 and 34 will be reviewed to determine the cause and establish whether the delivery was because of medical indication or spontaneous. Spontaneous deliveries will include those with prior preterm labor and those with rupture of membranes before the onset of labor. Quality control for screening, information management, and monitoring of adherence to protocol across the four sites will be performed regularly by the clinical study monitor.

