## 8 ADVERSE EVENTS

An adverse experience is defined as an unfavorable and unexpected change in the structure, function, or chemistry of the body, transiently associated with the use of the study product, whether or not related to the use of the drug. Any worsening (i.e., any adverse change clinically significant in terms of frequency or severity) of a pre-existing condition that is transiently associated with use of the study product is also an adverse experience.

Adverse events will be documented from the time of enrollment (i.e., at the time of signing the informed consent form) through the last scheduled contact as per the protocol, i.e., the date of the last visit/contact (may be a phone call, for example, in case the participant withdraws from the study).

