### Definition of Serious Adverse Event (SAE)

A SAE is any medical incidence that, at any dose:

- Results in death; or
- Is life-threatening (puts the subject, from the investigator's perspective, in an immediate risk of death due to the experience that took place. This includes direct life-threatening experiences but not those that could potentially put life at risk), or
- Requires or prolongs hospitalization of the patient (hospitalization is defined as an admission, regardless of length of stay, even if hospitalization is a precautionary measure in order to continuously monitor the patient). If this hospitalization is due to a non-worsening pre-existing condition, it is not to be considered as a serious adverse experience.

- Results in persistent or significant inability/disability (major impairment to the ability to perform daily life functions); or
- Is an abnormal congenital defect or birth defect
- Is considered a clinically significant medical event

A scheduled hospital admission, for example, for elective surgery, is not considered a SAE if documented at the time of enrollment.

All patients randomized in the study are pregnant women, therefore, hospitalizations related to scheduled parturitions/full term deliveries will not be considered as adverse events nor as serious or relevant adverse events.

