#### **Expected Adverse Events**

Expected Adverse Events will be evaluated by the Sponsor.

An unexpected adverse event is one where the nature or severity is not consistent with the information contained in the relevant source document, i.e. the Investigator Brochure.

In addition, reports that add significant information about the specificity or seriousness of a known, already documented adverse reaction are unexpected adverse events. For example, an adverse event more specific or more serious than expected would be considered "unexpected."

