Occurrence of membranes' ruptures: Premature rupture of membranes after 32 weeks but before 34 weeks of gestation. The Cochran-Mantel-Haenszel (CMH) test will be used, where the incidence of rupture of membranes in each group will be compared and will be identified through the registration of adverse events.

Anatomical cervical changes (Only groups B and C): The length of the cervix and cervical angle variables, will be described as continuous and measured variables through time, using the test of comparison of means through the Analysis of Variance (ANOVA) for repeated measures, considering the baseline result as a covariate in the comparison and shall be based on the sum of squares type III. The difference between groups regarding the change from baseline will be assessed through t tests paired within ANOVA, utilizing the difference in means estimated by least squares. These comparisons will be made amongst all treatment groups with pessary.

Acceptability and tolerability of insertion (only groups B and C):

Acceptability and tolerability will be assessed through a questionnaire which must be completed at the beginning and end of the study. Questions (i) and (ii) are answered at visit 1, question iii (VAS) is answered at visit 1 and final visit, and questions (iv) to (ix) are answered at the final visit.

It is composed of several items

- (i) Ease of insertion (visit 1). This question has the following categories: 1 = very good, 2 = good, 3 = regular, 4 = bad and 5 = very bad; and only one of them will be selected.
- (ii) Subjects pain at the time of insertion (visit 1). This question has the following categories: 1 = without pain, 2 = with little pain, 3 = with moderate pain, 4 = with intense pain and 5 = with unbearable pain; and only one of them will be selected.

- (iii) Visual Analog Scale of pain (VAS) (visit 1 and final visit): this scale is evaluated in 10 points where 10 represents the worst pain suffered during her lifetime and 1 the absence of pain.

Analysis for the VAS will be described as continuous and measured variables through time using the test of comparison of means through the Analysis of Variance (ANOVA) and must be based on the sum of squares type III. The treatment differences regarding the change from baseline, will be assessed through t tests paired within ANOVA, utilizing the difference in means estimated by least squares. These comparisons will be made amongst all treatment groups.

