11. SAFETY ANALYSIS

11.1 ADVERSE EVENTS

The evaluation of adverse events (AE) will be monitored throughout the study, by direct observation at each visit.

All AE will be recorded (according to the definition), and not only those where the investigator suspects a causal relationship with the treatment. Adverse events of interest; i.e., those in which the investigator at each site must pay particular attention are those that have been defined as local safety (pain, irritation, itching and infection) and major maternal complications attributable to the pessary as chorioamnionitis, severe vaginal or cervical trauma.

All the AE will be encoded in MedDRA version 19.1 or higher to be summarized by System Organ Class (SOC) / Preferred Term (PT).

The following 3 overview tables will be generated by treatment group and overall:

1) Summary of the number and percentage of subjects with at least 1:

- AE
- Serious AE
- Non-serious AE
- Unexpected AE
- Severe AE
- Related AE
- Related serious AE
- AE leading to discontinuation from IMP

The percentage denominator will be the number of subjects in the safety analysis.

2) Summary presenting the number of AEs per subject categorized as 0, 1, 2, 3, 4, 5, and >5;

3) Summary of the number and percentage of AEs for:

- AEs
- Serious AEs
- Non-serious AEs
- Unexpected AEs
- Related AEs
- Related serious AEs
- AEs leading to discontinuation from IMP

The percentage denominator will be the total number of AEs.

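### Rupture of membranes is counted only from adverse event records, a weak source for a between-arm efficacy comparison in an open-label trial

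*SAP*

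**What the plan says.** Rupture of membranes is the first secondary outcome in Protocol section 7.2. SAP section 10 (Secondary analysis) compares its incidence between groups with a CMH test and says that it "will be identified through the registration of adverse events".

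The text that decides what enters those records is spread over both documents:

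- **Definition.** Protocol section 8 describes an adverse experience as "an unfavorable and unexpected change in the structure, function, or chemistry of the body". Its next sentence adds worsening of a pre-existing condition.
- **Recording rule.** SAP section 11.1 refers back to that definition: "All AE will be recorded (according to the definition".
- **Expected events.** The protocol also has a heading for these: "Expected Adverse Events will be evaluated by the Sponsor".
- **Serious events.** Any medical incidence qualifies if, among other criteria, it "Requires or prolongs hospitalization of the patient".
- **Period.** Adverse events are documented from consent "through the last scheduled contact as per the protocol, i.e., the date of the last visit/contact".
- **After removal.** SAP section 9 terminates a woman early from the study if the pessary has to be removed. Protocol section 5.7 says that women withdrawn from the product have the standard follow-up.
- **Pregnancy outcome.** Protocol section 5.8 takes this from the hospital's "medical records file or treating physician".

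**The concern.** An efficacy endpoint needs the same active ascertainment in every arm. Adverse event registration depends on a site deciding that something is an adverse event, and here the site knows the treatment. Read alone, the first sentence of the definition lets a site reason that rupture is not unexpected in a woman enrolled because she is at risk of it.

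Collection also depends on the woman still being in contact with the study, and the triggers for withdrawal differ between pessary and capsules. If capture differs by arm, the comparison mixes a treatment effect with a recording effect. Nothing in the analysis could separate them.

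**Working it through.** **Is there another route by which rupture must be recorded?**

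| Place | Does it ensure that rupture is captured? |
|---|---|
| SAP section 10 | Names adverse event registration and nothing else |
| SAP Table 1, footnote 4 (birth items) | Lists medication, admissions, delivery, newborn and neonatal items, but not rupture |
| Protocol section 8, events of special interest | Names preterm birth only |
| SAP section 11.1, events of interest | Names local effects, chorioamnionitis and trauma, but not rupture |
| Protocol section 8, serious events | Yes, if the woman is admitted; no condition that the event be unexpected |
| Protocol section 5.8, review of records | Only for preterm labour before weeks 32 and 34, to classify the delivery; a rupture before 34 weeks followed by a later delivery falls outside it |

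Capture is therefore likely for ruptures that lead to admission while the woman is in the study. No text written for this endpoint requires it.

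**Is the definition consistent?** No. Its first sentence requires an unexpected change. The protocol nonetheless provides for expected adverse events and judges expectedness against the Investigator Brochure. SAP section 11.1 tabulates unexpected events as a subset of all events, which makes sense only if expected ones are recorded too.

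**Does collection continue after withdrawal?** Unclear. SAP section 9 and Protocol section 5.7 point different ways, and section 5.7 does not say whether standard follow-up includes adverse event recording for the study.

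**Size.** The plan gives no rupture rate, no capture rate and no withdrawal rate by arm, so there is no figure of its own to reproduce. Its 90 per group was set for spontaneous birth. The following is an illustration only.

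Inputs: 90 per arm and two-sided alpha 0.05 (documents); equal true rate π in both arms, and capture c₁ and c₂ (assumed).

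- Observed rates: a = π·c₁ and b = π·c₂. The apparent risk ratio is b/a = c₂/c₁.
- p̄ = (a + b)/2; se₀ = √(2·p̄(1 − p̄)/90); se₁ = √(a(1 − a)/90 + b(1 − b)/90).
- False-positive rate = 1 − Φ((1.96·se₀ − (a − b))/se₁) + Φ((−1.96·se₀ − (a − b))/se₁).

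Example with π = 0.10, c₁ = 1, c₂ = 0.8: a = 0.10 and b = 0.08 (9.0 against 7.2 expected events). Then p̄ = 0.09, se₀ = 0.0427, se₁ = 0.0426 and 1.96·se₀ = 0.0836. The two standardised limits are 1.492 and −2.430, so the rate is 0.0679 + 0.0075 = 0.0754.

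| True rate, both arms | 100% v 90% capture (ratio 0.90) | 100% v 80% (ratio 0.80) | 100% v 60% (ratio 0.60) |
|---|---|---|---|
| 5% | 5.3% | 6.2% | 10.5% |
| 10% | 5.6% | 7.5% | 16.7% |
| 20% | 6.3% | 10.7% | 30.9% |
| 30% | 7.3% | 14.8% | 47.0% |

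The 90% column matches the plan's allowance of up to 10% not completing, if all of that loss fell in one arm and was unrelated to rupture risk. With 90% capture in both arms the ratio is 1.00 and the error 5.0%. Reversing 100% and 80% gives a ratio of 1.25 with the same error rates. This is a pairwise normal approximation, not the CMH test across three groups, and it is rough at the lowest counts.

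**The case against.** The strongest reply is that the records will in practice contain most ruptures. Even a precautionary admission makes the event serious, and preterm birth must be reported within 24 hours. The review in Protocol section 5.8 recognises rupture before labour among the deliveries it covers. This stands, and it keeps the point small.

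Three stronger readings are tempting, and the documents do not support them.

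- A reader might infer that the definition excludes rupture. It does not. Expected events are provided for, and expectedness is judged against the Investigator Brochure, not against a woman's obstetric risk. Nor are local effects at risk of omission, because SAP section 11.1 names pain, irritation, itching and infection as events of interest.
- A reader might infer that events are lost only in the pessary arms. Protocol section 5.6 also withdraws control women, for adherence below 80% or an interruption of more than 72 hours. For pessary women, Protocol section 5.7 promises continued follow-up, and SAP section 1 makes the protocol the final reference.
- A reader might put a size on a false benefit. If 8 of 90 women in each arm had a rupture and 2 or 3 went unrecorded in a pessary arm, the apparent reduction would be 1 − 6/8 = 25% or 1 − 5/8 = 37.5%. Those losses are invented, and the whole effect comes from assuming none among controls.

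The main efficacy set is also Per Protocol (SAP section 6). Women terminated early would generally leave both numerator and denominator there, so loss after termination matters mainly in the intention-to-treat analysis. The unclear definition affects both.

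**Conclusion.** The point holds as a weakness of source. A between-arm efficacy endpoint rests on a safety record that was not designed to capture it. The governing definition contradicts other text, and its collection period is unclear after pessary removal. In an open-label trial whose withdrawal triggers differ by arm, under-recording and unequal recording are both possible.

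Neither is demonstrated, and the documents fix no size or direction. Under the assumed rates above the effect runs from negligible (5.3% false positives at a 5% true rate with 90% capture in one arm) to serious (47.0% at a 30% true rate with 60% capture), and it disappears if capture is equal. This is a cheap improvement to a secondary endpoint and does not touch the primary analysis.

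**What to change.** 1. **SAP section 10:** take the occurrence, date and gestational age of rupture of membranes from the hospital record and delivery form for every randomised woman, regardless of product withdrawal. Use adverse event records as a cross-check.
2. **Protocol section 8:** delete the word unexpected from the first sentence of the definition, so that it agrees with the text on expected events and with SAP section 11.1.
3. **Protocol section 5.7 and SAP section 9:** reconcile the two on what data are collected after a pessary is removed. This concerns data collection only, not when a pessary should be removed.

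The cost is one added form item and a little more data checking. Sites already go to the hospital record or treating physician for pregnancy outcome, so no new source has to be set up.
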